3.2 DISCUSSION OF TRIAL DESIGN, INCLUDING THE CHOICE OF CONTROL GROUP(S)

There is an urgent public health need for development of treatments for COVID-19. This trial is designed to assess BI 764198 as a potential treatment for respiratory disease associated with COVID-19. Patients to be initiated in the study will be those hospitalised for COVID-19, but not yet needing tracheal intubation and mechanical ventilation.

The primary endpoint (patients alive and free of mechanical ventilation at Day 29) is a clinically meaningful outcome measure for an acute condition in which most patients will either die or substantially recover within a short time period.

The secondary endpoint of improvement on the WHO Clinical Progression Scale is an internationally recommended endpoint for assessing the efficacy of new treatments for patients with SARS-CoV-2 [R20-2002]. As patients may continue to worsen despite therapy, the study will also capture disease worsening prior to, or in the absence of, disease improvement.

A parallel group, randomized, double-blind, placebo-controlled trial is considered the most appropriate design to assess the efficacy and safety BI 764198. Therapy will be on top of usual care for COVID-19, so all patients will receive usual care.

A Data Monitoring Committee (DMC), which is independent of the sponsor except for the iSTAT, will be established for this study to assess safety on an ongoing basis throughout the study (see [Section 8.7](#)). The DMC members will perform ongoing safety surveillance and provide recommendations to the sponsor regarding study conduct. Further details are provided in the DMC charter.

3.3 SELECTION OF TRIAL POPULATION

Screening of patients for this trial is competitive, i.e. screening for the trial will stop at all sites at the same time once a sufficient number of patients has been screened. Investigators will be notified about screening completion and will then not be allowed to screen additional patients for this trial.

Patients over the age of 50 years are included as these patients have higher risk of developing severe lung complications or potentially dying as result of SARS-CoV-2 infection. Hence, the evaluation of the potential beneficial effects of TRPC6 inhibition in this high risk population would expose a smaller number of patients to this investigational compound in this clinical proof of concept study.

Patients are selected because they have been hospitalised for COVID-19 and are at risk of developing ARDS. Efforts should be made to minimize the time from patient identification to treatment, as TRPC6 inhibition is expected to provide benefit early in the course of disease. Patients that do not have the potential for key outcomes or are already improving should not be included.

A sufficient number of patients hospitalised for COVID-19 will be screened in multiple countries from approximately 40 trial sites to ensure the randomisation of approximately 130 eligible patients.

A log of all patients enrolled into the trial (i.e. who have signed informed consent) will be maintained in the Investigator Site File (ISF) irrespective of whether they have been treated with investigational drug or not.

If a patient is enrolled in error (does not meet all inclusion criteria or meets one or more exclusion criteria on the day of enrolment), the sponsor should be contacted immediately.

3.3.1 Main diagnosis for trial entry

Adult patients (≥ 50 years) hospitalised for COVID-19 requiring non-mechanical (ventilator) oxygen therapy and who comply with eligibility requirements may qualify for participation in this trial.

Please refer to [Section 8.3.1](#) (Source Documents) for the documentation requirements pertaining to the in- and exclusion criteria.

3.3.2 Inclusion criteria

1. Age ≥ 50 years
2. SARS-CoV-2 infection positive confirmed by PCR or approved point-of-care test.
3. A score of 5 (hospitalised; oxygen by mask or nasal prongs) or 6 (hospitalised; oxygen by non-invasive ventilation or high flow), but not previously ≥ 7 , on the WHO Clinical Progression Scale.
4. Signed and dated written informed consent in accordance with ICH-GCP and local legislation prior to admission to the trial.
5. Male or female patients. Women of childbearing potential (WOCBP)¹ and men able to father a child must abstain from male female sex or must use highly effective methods of birth control per ICH M3 (R2) that result in a low failure rate of less than 1% per year when used consistently and correctly during hospitalisation for at least 7 days after last trial drug intake. A list of contraception methods meeting these criteria is provided in [Section 4.2.2.3](#).

3.3.3 Exclusion criteria

1. Alanine aminotransferase (ALT)/aspartate aminotransferase (AST) $> 5 \times$ the upper limit of normal (ULN).
2. Known active infection with HIV or hepatitis B or C.
3. Pulmonary oedema/respiratory failure due to cardiogenic insult.
4. Long-term oxygen therapy prior to current hospitalisation.
5. A confirmed baseline prolongation of QTc interval to greater than 450 ms in males or 470 ms in females, or any other relevant ECG finding at screening, or continued use of agents known to prolong the QT interval (refer to listing provided in ISF).
6. Stage 4 kidney disease or requiring dialysis (i.e., eGFR < 30 mL/min/1.73 m²).
7. History of the following cardiac conditions:
 - a) Myocardial infarction within 3 months prior to the first dose

¹ A woman is considered of childbearing potential (WOCBP), i.e. fertile, following menarche and until becoming post-menopausal unless permanently sterile.

Permanent sterilisation methods include hysterectomy, bilateral salpingectomy and bilateral oophorectomy.

Tubal ligation is NOT a method of permanent sterilisation.

A postmenopausal state is defined as no menses for 2 years without an alternative medical cause.

Proprietary confidential information © 2021 Boehringer Ingelheim International GmbH or one or more of its affiliated companies

- b) Unstable angina
- c) Clinically significant long QT features on electrocardiogram (ECG) or history of familial long QT
- 8. Anticipated transfer/discharge to another hospital or care facility other than their place of residence.
- 9. Not committed to full support or intubation (do not resuscitate/do not intubate wishes)
- 10. Allergy to study medication.
- 11. Relevant end-organ failure or other medical conditions (e.g. active cancer, cardiac, gastrointestinal) which based on investigator judgement would interfere with the conduct of this study.
- 12. Experimental, or off-label usage of medicinal products as specific treatments for COVID-19.
- 13. Currently enrolled in another investigational device or drug trial, or less than 30 days or 5 half-lives (whichever is shorter) since ending another investigational device or drug trial(s), or receiving other investigational treatment(s).
- 14. Women who are pregnant, nursing, or who plan to become pregnant while in the trial.

3.3.4 Withdrawal of patients from treatment or assessments

Patients may discontinue trial treatment or withdraw consent to trial participation as a whole (“withdrawal of consent”) with very different implications; please see [Section 3.3.4.1](#) and [Section 3.3.4.2](#) below.

Every effort should be made to keep the patients in the trial: if possible on treatment, or at least to collect important trial data.

Measures to control the withdrawal rate include careful patient selection, appropriate explanation of the trial requirements and procedures prior to trial enrolment, as well as the explanation of the consequences of withdrawal.

The decision to discontinue trial treatment or withdraw consent to trial participation and the reason must be documented in the patient files and CRF. If applicable, consider the requirements for Adverse Event collection reporting (please see [Sections 5.2.6.2.1](#) and [5.2.6.2](#)).

3.3.4.1 Discontinuation of trial treatment

An individual patient will discontinue trial treatment if:

- The patient wants to discontinue trial treatment, without the need to justify the decision.
- The patient has repeatedly shown to be non-compliant with important trial procedures and, in the opinion of both, the investigator and sponsor representative, is not willing or able to adhere to the trial requirements in the future.
- The patient needs to take concomitant medication that interferes with the investigational medicinal product or other trial treatment.
- The patient can no longer receive trial treatment for medical reasons (such as surgery, adverse events, other diseases, or pregnancy).

Proprietary confidential information © 2021 Boehringer Ingelheim International GmbH or one or more of its affiliated companies

- The patient experiences renal impairment based on clinical judgement (e.g. sustained eGFR <30 mL/min/1.73 m²).
- The patient experiences hepatic impairment based on clinical judgement (e.g. ALT/AST >5 × ULN).
- The patient experiences QT prolongation of the QTc interval of either >60 ms change from baseline or greater than 500 ms during the study.

Should a patient become pregnant during the trial, study medication will be stopped and the patient will be followed up until birth or otherwise termination of the pregnancy. The data of the patient will be collected until Last Patient Completed and reported in the clinical trial report. Any events thereafter will be reported in the BI Pharmacovigilance database. For further details on pregnancy reporting, refer to [Section 5.2.6.2.3](#).

If new efficacy/safety information becomes available, Boehringer Ingelheim will review the benefit-risk-assessment and, if needed, pause or discontinue the trial treatment for all patients or take any other appropriate action to guarantee the safety of the trial patients.

Even if the trial treatment is discontinued, the patients remain in the trial and, given their agreement, will undergo the procedures for early treatment discontinuation, follow-up, and vital status collection as outlined in the [Flow Chart](#) and [Section 6.2.3](#).

3.3.4.2 Withdrawal of consent to trial participation

Patients may withdraw their consent to trial participation at any time without the need to justify the decision.

If a patient wants to withdraw consent, the investigator should be involved in the discussion with the patient and explain the difference between trial treatment discontinuation and withdrawal of consent to trial participation, as well as explain the options for continued follow-up after trial treatment discontinuation, please see [Section 3.3.4.1](#) above.

3.3.4.3 Discontinuation of the trial by the sponsor

Boehringer Ingelheim reserves the right to discontinue the trial overall or at a particular trial site at any time for the following reasons:

1. Failure to meet expected enrolment goals overall or at a particular trial site.
2. New efficacy or safety information invalidating the earlier positive benefit-risk-assessment, please see [Section 3.3.4.1](#).
3. Deviations from GCP, the trial protocol, or the contract impairing the appropriate conduct of the trial.

Further follow up of patients affected will occur as described in [Section 3.3.4.1](#).

The investigator / the trial site will be reimbursed for reasonable expenses incurred in case of trial termination (except in case of the third reason).

4. TREATMENTS

4.1 INVESTIGATIONAL TREATMENTS

BI 764198 and placebo to match BI 764198

4.1.1 Identity of the Investigational Medicinal Products

Table 4.1.1: 1 Test product 1

| | |
|-----------------------------|--|
| Substance: | BI 764198 |
| Pharmaceutical formulation: | Capsule |
| Source: | Boehringer Ingelheim Pharma GmbH & Co KG |
| Unit strength: | [REDACTED] |
| Posology | q.d. |
| Route of administration: | Oral (p.o.) or, only if needed, nasogastric intubation |

Table 4.1.1: 2 Test product 2

| | |
|-----------------------------|--|
| Substance: | Placebo to match BI 764198 |
| Pharmaceutical formulation: | Capsule |
| Source: | Boehringer Ingelheim Pharma GmbH & Co KG |
| Unit strength: | Not applicable |
| Posology | q.d. |
| Route of administration: | Oral (p.o.) or, only if needed, nasogastric intubation |

4.1.2 Selection of doses in the trial and dose modifications

The proposed therapeutic dose in patients hospitalised with COVID-19 is [REDACTED] once daily; a dose expected to achieve maximal therapeutic benefits. The rationale for the selection of this dose is based on the following considerations (refer to [Section 1.2](#)):

4.1.3 Method of assigning patients to treatment groups

After the assessment of all inclusion and exclusion criteria, each eligible patient will be randomised to treatment groups according to a randomisation plan in a 1:1 ratio at Visit 2 via Interactive Response Technology (IRT). Note that the medication number is different from the patient number (the latter is generated during screening via the IRT System).

4.1.4 Drug assignment and administration of doses for each patient

Study medication will be administered, according to the [Flow Chart](#), by a member of the site staff that is qualified and licensed to administer the study drug. During the treatment period, patients are hospitalised and study medication will be administered once daily after the other visit procedures have been performed. Study drug should be administered after at least 6 hours fasting (no food, water is allowed). Patients should remain fasted for 1.5 hours after study drug administration. Therefore, it is recommended to dose patients after overnight fast, 1.5 hours prior to breakfast meal intake.

For administration of study medication on Day 1, the following guidance may be followed to allow flexibility in the emergency care setting to begin treatment as soon as feasibility after study qualification:

- While 6 hours of fasting is preferred, a minimum of 2 hours is allowed in order to dose an eligible patient as soon as feasible following completion of screening
- It would be preferred to maintain a 12-18 hour interval between the doses
- If the patient is dosed before 18:00, the next dose should be a morning fasted dose the next day (followed by morning dosing thereafter)
- If the patient is dosed before midnight, the next dose should be at about noon the next day (followed by morning dosing thereafter)

The route of administration is oral (p.o.) or, only if needed, nasogastric intubation (refer to investigator site file (ISF) for dissolution preparation and administration instructions). If a patient is on continuous nasogastric feeding, the need to meet caloric requirements should be prioritized and it is recommended that feeding only be interrupted for the duration needed to administer the drug.

Proprietary confidential information © 2021 Boehringer Ingelheim International GmbH or one or more of its affiliated companies

Trial treatment may be restarted after a temporary reason for treatment discontinuation. Dose reductions or down-titrations are not allowed.

Patients will be administered one capsule per day from Visit 2 until the visit prior to EOT Visit. Patients may receive treatment with study drug for up to 28 days. In [Table 4.1.4: 1](#), the medication schedule for each treatment group is listed.

Table 4.1.4: 1 Dosage and treatment schedule

| | |
|----------------------------|--|
| | [REDACTED] or matching placebo capsule |
| [REDACTED] treatment group | 1 active |
| Placebo group | 1 placebo |

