| Blood Gases/PaO ₂ data capture if performed as part of routine care | X | X | X | X | | | |
| 12-lead ECG ^{c,g} | X | X (±1 day) | Day 3,7,14,21 (±1 day) | X | | | |
| Physical Exam (refer to Section 5.2.1) | X | X (±1 day) | Day 3,7,14,21 (±1 day) | X | | | |
| Safety Laboratory Samples (refer to Section 5.2.3) ^{c,d} | X | X (±1 day) | Day 3,7,14,21 (±1 day) | X | | | |
| Pregnancy test (blood) for WOCBP ^{c,d} | X | | Day 7,14 (±1 day) | X | | | |
| Administration of trial medication ^e | | X | X | X ⁱ | | | |
| Termination of trial medication | | | | X | | | |
| Trial Completion | | | | | | | X |
| Vital Status | | | | | X | X | X |

EOT=End of Treatment; EOS=End of Study; FiO₂=fraction of inspired oxygen; FUP=Follow-up; PCR=polymerase chain reaction; PO₂=partial pressure of oxygen; SARS-CoV-2= severe acute respiratory syndrome coronavirus 2.

Footnotes:

^a EOT visit should be completed the day after the last dose of study drug is administered for all patients. EOT visit should occur no later than Day 29.

^b FUP 1 should be performed 4 days after EOT visit for all patients. FUP 2 and FUP 3 which correspond to study Day 15 and Day 29 after start of therapy, should be performed *if the time point is applicable after drug discontinuation*. FUP 2 and FUP 3 visits should not be conducted within +/- 2 days of EOT or FUP 1. FUP 4 and EOS which correspond to study Day 60 and Day 90 will be performed for all patients. If a patient remains hospitalized after EOT visit, applicable FUP visits and

Proprietary confidential information © 2021 Boehringer Ingelheim International GmbH or one or more of its affiliated companies

the EOS visit will be conducted in hospital until discharge and thereafter by telephone. Refer to [Section 6.2.3](#).

^c Laboratory tests and ECG performed up to 72 hours prior to enrolment will be accepted for determination of eligibility and the screening visit date may be the same day as Visit 2 or up to 3 days prior to Visit 2.

^d Results from laboratory tests performed as part of routine clinical care within the specified visit window may be used.

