^e Interactive Response Technology (IRT) will be used to allocate a 10 day supply of study drug at Visit 2 (or at the conclusion of Visit 1 after all eligibility criteria are confirmed to be met to allow time to prepare the study drug prior to day of randomization (first administration of study drug) and, if applicable per an individual patient's treatment duration, at Visit 12 and Visit 22.

^f If the patient discontinues treatment and is not discharged prior to Day 29, collect ventilation and oxygen parameters daily up to Day 29, respiratory rate, FiO₂, SpO₂, if applicable, at Day 29, and WHO Clinical Progression Scale score at Day 29. If patient is on oxygen therapy at discharge, collect end date of that oxygen therapy when available during the Follow-up visit telephone call(s).

^g ECG should be performed 0.5-4 hours after drug administration.

^h SARS-CoV-2 PCR test to be performed as visit procedure and an approved SARS-CoV-2 point-of-care test may be used to evaluate inclusion criterion 2, refer to [Section 3.3.2](#).

ⁱ Dosing should be stopped the day prior to EOT. However, if it is uncertain whether a patient is fit for discharge, and the patient has not yet completed the allowed treatment duration of 28 days, administer study drug and perform all study procedures per the planned treatment period visit. If later that day the PI makes the decision that patient will discharge, perform any additional EOT visit procedures, if applicable, per [Flow Chart](#) and record visit in the eCRF as EOT visit.

TABLE OF CONTENTS

| | |
|---|-----------|
| TITLE PAGE | 1 |
| CLINICAL TRIAL PROTOCOL SYNOPSIS | 2 |
| FLOW CHART | 4 |
| TABLE OF CONTENTS | 6 |
| ABBREVIATIONS | 9 |
| 1. INTRODUCTION..... | 12 |
| 1.1 MEDICAL BACKGROUND | 12 |
| 1.2 DRUG PROFILE | 13 |
| 1.3 RATIONALE FOR PERFORMING THE TRIAL | 15 |
| 1.4 BENEFIT - RISK ASSESSMENT..... | 16 |
| 1.4.1 Benefits | 16 |
| 1.4.2 Risks | 16 |
| 1.4.3 Discussion..... | 17 |
| 2. TRIAL OBJECTIVES AND ENDPOINTS..... | 18 |
| 2.1 MAIN OBJECTIVES, PRIMARY AND SECONDARY ENDPOINTS..... | 18 |
| 2.1.1 Main objectives..... | 18 |
| 2.1.2 Primary endpoint(s)..... | 18 |
| 2.1.3 Secondary endpoints | 18 |
| [REDACTED] | |
| 3. DESCRIPTION OF DESIGN AND TRIAL POPULATION..... | 20 |
| 3.1 OVERALL TRIAL DESIGN..... | 20 |
| 3.2 DISCUSSION OF TRIAL DESIGN, INCLUDING THE CHOICE OF CONTROL GROUP(S)..... | 20 |
| 3.3 SELECTION OF TRIAL POPULATION | 21 |
| 3.3.1 Main diagnosis for trial entry | 22 |

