| Coagulation | D-dimer test Fibrinogen Activated partial thromboplastin time (aPTT) Prothrombin time (PT) International Normalised Ratio (INR) Protein C (activity as well as antigen, if available) Plasminogen activator inhibitor-1 (PAI-1) (activity) |
| Clinical Chemistry | Potassium Sodium Calcium Magnesium Phosphate Alkaline phosphatase Bicarbonate Creatinine Creatine kinase (MB fraction) eGFR (estimated by the CKD-EPI formula) Glucose Total bilirubin Aspartate aminotransferase (AST) Alanine aminotransferase (ALT) Gamma-glutamyl transferase (GGT) C-reactive protein (regular test) Ferritin Triglycerides Lactate dehydrogenase (LDH) Troponin (I) |

5.2.4 **Electrocardiogram**

The 12-lead ECGs must be administered by a qualified technologist and results will be recorded as scheduled in the [Flow Chart](#). ECGs should be performed 0.5-4 hours after drug administration. The investigator or a designee will evaluate whether the ECG is normal or abnormal and assess clinical relevance. ECGs may be repeated for quality reasons and a repeated recording used for safety evaluation.

Additional ECGs may be recorded for safety reasons. Dated and signed printouts of ECG with findings should be documented in patient's medical record. The aggregate PR, QRS, QT, RR, QTcF, and QTcB interval data, as available, from the local ECG readout will be recorded in the eCRF for safety evaluation.

Clinically relevant abnormal findings will be reported either as baseline condition (if identified at the screening visit) or otherwise as AEs and will be followed up and/or treated as medically appropriate.

Refer to [Section 3.3.4.1](#) for treatment discontinuation criteria regarding QT prolongation.

5.2.5 **Other safety parameters**

Not applicable

5.2.6 **Assessment of adverse events**

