6.2 DETAILS OF TRIAL PROCEDURES AT SELECTED VISITS

Study procedures to be performed at each visit are listed in the [Flow Chart](#) and explanations provided in [Section 5](#). Additional details on procedures at selected visits are provided below.

At all applicable visits vital signs, blood gases and WHO Clinical Progression Scale assessment should be done prior to study drug administration.

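### Protocol Section 4.1.4 puts the daily dose after the other visit procedures, while the Flow Chart and Section 5.2.4 put the ECG 0.5-4 hours after the dose; on ECG days a site cannot follow both.

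*Protocol*

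**What the plan says.** Five places in the protocol bear on the order of ECG and dose.

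- Section 4.1.4 (drug assignment and administration): "study medication will be administered once daily after the other visit procedures have been performed". The sentence before it says that dosing follows the Flow Chart. Neither sentence mentions the ECG.
- Flow Chart, 12-lead ECG row: an ECG at screening, at Visit 2 (Day 1, ±1 day), on Days 3, 7, 14 and 21 (±1 day), and at end of treatment (EOT). The row label carries footnote g: "ECG should be performed 0.5-4 hours after drug administration".
- Section 5.2.4 (Electrocardiogram) repeats the timing: "ECGs should be performed 0.5-4 hours after drug administration".
- Section 6.2 names the procedures that must precede the dose: "At all applicable visits vital signs, blood gases and WHO Clinical Progression Scale assessment should be done prior to study drug administration". The ECG is not among them.
- Section 3.3.4.1 lists, among the reasons to stop trial treatment, "QT prolongation of the QTc interval of either >60 ms change from baseline or greater than 500 ms".

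SAP Section 7.8.4 plans descriptive ECG summaries, with additional summaries for patients above the sex-specific QTc thresholds. It does not take account of time since dose.

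**The concern.** The ECG is a scheduled visit procedure on dosing days. If the dose comes after the other visit procedures, the ECG comes before the dose. If the ECG comes 0.5-4 hours after the dose, the dose is not last. A single scheduled ECG cannot meet both instructions.

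The stake is safety monitoring. The protocol chose a post-dose window for its ECGs and has a QTc criterion for discontinuation. Where the dose is always given last, no scheduled ECG would fall in that window, and the routine readings that feed the criterion would come from a different part of the dosing interval than the one the protocol specifies. The SAP summaries would not show this, because they do not separate readings by time since dose.

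**Working it through.** There is no sample size, power or alpha figure to reproduce. The check compares passages of the current text and adds a short calculation of time since dose.

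**Step 1: which ECGs are affected.** The conflict needs a scheduled ECG and a dose on the same day. The Flow Chart gives Day 1 plus Days 3, 7, 14 and 21, so 1 + 4 = 5 occasions at most. Patients whose treatment ends earlier have fewer. The screening ECG precedes any dose. EOT is normally the day after the last dose: "EOT visit should be completed the day after the last dose of study drug is administered for all patients". Footnote i allows an exception, where a day on which drug was given is later recorded as EOT.

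**Step 2: whether the day window helps.** The ±1 day allowance moves the ECG to another day. If that is also a treatment day, the same order of procedures applies, so the conflict remains.

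**Step 3: the two readings side by side.**

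| Scheduled ECG | Section 4.1.4 taken literally | Footnote g and Section 5.2.4 |
|---|---|---|
| Day 1 | Before any drug | 0.5-4 h after the first dose |
| Day after the first dose, where the ±1 day allowance places an ECG there | About 12-18 h after the first dose, if the interval preferred in 4.1.4 is kept | 0.5-4 h after that day's dose |
| Later days, regular morning dosing | About 24 h after the previous dose | 0.5-4 h after that day's dose |

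Under regular 24-hour dosing the two readings differ by 24 − 4 = 20 h to 24 − 0.5 = 23.5 h. On the day after the first dose the literal reading still gives at least about 12 h, against an upper limit of 4 h. The literal reading of 4.1.4 therefore never falls in the window.

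**Step 4: whether other text removes the conflict.** Section 6.2 requires only vital signs, blood gases and the WHO scale before the dose. That is compatible with a post-dose ECG, but it does not cancel the broader clause in 4.1.4. The reference to the Flow Chart in 4.1.4 points to a document that carries footnote g, and the next sentence then sets a conflicting order. Section 4.1.4 says what will be done, while the ECG passages say what should be done, so the strength of the wording does not settle which governs.

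**Step 5: reliance on the amendment log.** None. All the passages compared are current operative text.

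**The case against.** The strongest reply is that the protocol, read as a whole, already steers sites. Section 4.1.4 defers to the Flow Chart, the ECG timing is stated explicitly in two places, and Section 6.2 leaves the ECG off the pre-dose list. Three specific provisions fit together and one general clause does not, so many sites would probably follow the explicit ECG timing. QT safety also does not rest on scheduled ECGs alone: the stopping criterion applies throughout the study, and Section 5.2.4 allows additional ECGs for safety reasons.

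Much of this stands. It makes the consequence conditional on how sites read the text, and it limits the importance of the point. It does not remove the clause, which is a direct instruction to the staff who give the drug and has no ECG exception.

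A reader might infer more than the documents support:

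- **That QTc data will be a mixture of two exposure states by site.** This requires some sites to set aside both explicit ECG instructions. Nothing in the documents shows that they would, and the site file is not available for review.
- **That a site following 4.1.4 would take every ECG about 24 hours after the previous dose.** This fails on Day 1, when no drug has been given, and around the first doses, where the preferred interval is 12-18 hours.
- **That the EOT ECG is a second contradiction of equal weight.** Footnote g is attached to the row label, and that row includes screening, where no dose exists. The natural reading is that the timing applies on dosing days. This needs a clarification only.

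**Conclusion.** The inconsistency is real and lies in current text. On up to five scheduled dosing-day ECGs per patient, Section 4.1.4 cannot be followed together with footnote g and Section 5.2.4. Taken literally, 4.1.4 puts the Day 1 ECG before any drug and later ECGs roughly 12-24 hours after the previous dose, outside the 0.5-4 hour window. The scheduled ECGs that inform the QTc discontinuation criterion could then miss that window.

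The conclusion rests on two assumptions: that the ECG counts as one of the other visit procedures, as its place in the Flow Chart indicates, and that dosing is once daily as described. The number of sites affected cannot be known. No QTc effect can be sized, because the drug-profile text is redacted and the visible text gives no time of peak concentration. The window is taken as important only because the protocol itself specifies it.

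The primary endpoint is not affected. The point should be corrected because it concerns a safety-monitoring instruction that cannot be carried out as written, and the correction is cheap.

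**What to change.** Reconcile the Flow Chart ECG row and footnote g with Sections 4.1.4, 5.2.4 and 6.2, so that one order of ECG and dose applies on dosing days. Which order applies is for the sponsor to decide. State in footnote g that its timing refers to dosing days, since screening and, normally, EOT have no same-day dose. Notify sites of the clarified order.

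Optionally, report time since last dose alongside the QTc summaries in SAP Section 7.8.4. Protocol Section 4.3 puts dose date and time in the eCRF, but Section 5.2.4 mentions only dated printouts and interval data for the ECG. It should first be confirmed that ECG clock time is captured; if it is not, this option would need an added data item.

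The core change costs a wording correction in the passages concerned and a site notice. It adds no procedure and does not alter the efficacy analyses.
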